5.2.2 Static Physician's Global Assessment

The sPGA is a 5-point score ranging from 0 to 4, based on the physician's assessment of the average thickness, erythema, and scaling of all psoriatic lesions. The assessment is considered "static", which refers to the subject's disease state at the time of the assessments, without comparison to any of the subject's previous disease states (dynamic), whether at Baseline or at a previous visit (Appendix 10.2, [Figure 10.2: 1](#)).

A lower score indicates less body coverage, with 0 being clear and 1 being almost clear.

Erythema (0) Normal (Post-inflammatory hyperpigmentation may be present)
(1) Pink coloration of lesions
(2) Light red coloration of lesions
(3) Dull to bright red coloration of lesions
(4) Bright to deep red coloration of lesions

Induration (0) None
(1) Just detectable
(2) Mild thickening
(3) Clearly distinguishable to moderate thickening
(4) Severe thickening with hard edges

Scaling (0) No scaling
(1) Minimal focal scaling
(2) Predominately fine scaling
(3) Moderate scaling
(4) Severe /coarse scaling covering almost all or all lesions

Scoring:

Clear 0 = 0 for all 3
Almost clear 1 = mean > 0, < 1.5
Mild 2 = mean >= 1.5, < 2.5
Moderate 3 = mean >= 2.5, < 3.5
Severe 4 = mean >= 3.5

5.2.3 Dermatology Life Quality Index

The DLQI is a subject-administered, ten-question, quality of life questionnaire that covers 6 domains including symptoms and feelings, daily activities, leisure, work and school, personal relationships and treatment ([R05-2548](#)). The DLQI has a one-week recall period. Item scores range from 0 (not relevant) and 1 (not at all) to 3 (very much). Question 7 is a “yes”/ “no” question where “yes” is scored as 3.

The DLQI will be self-administered by the patient at visits indicated in the [Flow Chart](#).

The DLQI will be analyzed under 6 headings as follows ([R05-2548](#)):

Domain	Question Number	Score
Symptoms and feelings	Questions 1 and 2	Score maximum 6
Daily activities	Questions 3 and 4	Score maximum 6
Leisure	Questions 5 and 6	Score maximum 6
Work and school	Question 7	Score maximum 3
Personal relationships	Questions 8 and 9	Score maximum 6
Treatment	Question 10	Score maximum 3

DLQI total score is calculated by summing the scores of each question resulting in a range of 0 to 30 where 0-1 = no effect on subject’s life, 2-5 = small effect, 6-10 = moderate effect, 11-20 = very large effect, and 21-30 = extremely large effect on subject’s life. The higher the score, the more the quality of life is impaired. If the answer to 1 question in a domain is missing, that domain is treated as missing. If 2 or more questions are left unanswered (missing), DLQI total score is treated as missing. A 5-point change from Baseline is considered a clinically important difference ([Figure 10.2: 3](#)).

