5.1.2 Secondary Endpoints

Secondary endpoints are:

Efficacy

- Proportion of patients with a PASI 75 response at Week 24
- Mean percentage improvement in PASI at Week 16
- Proportion of patients with a sPGA \leq 1 (clear or almost clear) at Week 16
- Proportion of patients achieving a Dermatology Life Quality Index (DLQI) of 0 or 1 at Week 16

Safety

- Proportion of patients with drug-related AEs

Safety

- Proportion of patients with AEs, SAEs and AEs of Special Interest (AESIs) (e.g., serious infections and hypersensitivity reactions);

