10.2 EFFICACY ASSESSMENTS

Score	Short description	Detailed description
0	clear	No signs of psoriasis Post-inflammatory hyperpigmentation may be present
1	almost clear	Normal to pink coloration No thickening No to minimal focal scaling
2	mild	Pink to light red coloration Just detectable to mild thickening Predominantly fine scaling
3	moderate	Dull to bright red coloration Clearly distinguishable to moderate thickening Moderate scaling
4	severe	Bright to deep dark red coloration Severe thickening with hard edges Severe coarse scaling covering almost all or all lesions

Figure 10.2: 1 sPGA Rating Scale for Overall Psoriatic Disease

Body Segment	% of Total BSA	Anterior Sites Affected (% of Total BSA)		Posterior Sites Affected (% of Total BSA)	Row percentage total (%)
Head	10%		+		
Trunk	30%		+		
Upper Limbs	20%		+		
Lower Limbs	40%		+		
Total	100%				

Figure 10.2: 2 Body Surface Area Involved in Psoriasis

DERMATOLOGY LIFE QUALITY INDEX

Hospital No: _____ Date: _____
 Name: _____ Score:
 Address: _____ Diagnosis: _____

The aim of this questionnaire is to measure how much your skin problem has affected your life OVER THE LAST WEEK. Please tick one box for each question.

1.	Over the last week, how itchy, sore, painful or stinging has your skin been?	Very much  A lot  A little  Not at all 	
2.	Over the last week, how embarrassed or self conscious have you been because of your skin?	Very much  A lot  A little  Not at all 	
3.	Over the last week, how much has your skin interfered with you going shopping or looking after your home or garden ?	Very much  A lot  A little  Not at all 	Not relevant 
4.	Over the last week, how much has your skin influenced the clothes you wear?	Very much  A lot  A little  Not at all 	Not relevant 
5.	Over the last week, how much has your skin affected any social or leisure activities?	Very much  A lot  A little  Not at all 	Not relevant 

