10.1. DERIVATIONS

- Conversion factors:
 - 1 lbs=0.453592 kg
 - 1 in=2.54 cm
- BMI (kg/ m²) = weight (kg)/ height (m²)
- DLQI

The questionnaire will be analysed under 6 headings as follows:

Domain	Question Number	Score
Symptoms and feelings	Questions 1 and 2	Score maximum 6
Daily activities	Questions 3 and 4	Score maximum 6
Leisure	Questions 5 and 6	Score maximum 6
Work and school	Question 7	Score maximum 3
Personal relationships	Questions 8 and 9	Score maximum 6

Document: \\eedc-nas01a:\Boehringer_Ingelheim\BI_695501\XXA39605\Biostatistics\Documentation\SAP\15-v2.0\BI 1297.12 SAP v2.0 31JAN2018.docx

Author: Version Number: 2.0
Version Date: 31JAN2018

Template No: CS_TP_BS016 Revision 4
Effective Date: 01Apr2016

Reference: CS_WI_BS005

Treatment	Question 10	Score maximum 3
-----------	-------------	-----------------

Every item score ranges from 0 (Not relevant/Not at all) to 3 (Very much). The domain score is obtained by summing the score of the corresponding items.

DLQI total score is calculated by summing the scores of each question resulting in a range of 0 to 30 where 0-1 = no effect on subject's life, 2-5 = small effect, 6-10 = moderate effect, 11-20 = very large effect, and 21-30 = extremely large effect on subject's life. The higher the score, the more the quality of life is impaired. If the answer to 1 question in a domain is missing, that domain is treated as missing and the score calculated by summing the score of the 5 non-missing domains. If 2 or more questions are left unanswered (missing), DLQI total score is treated as missing.

-

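### Protocol 5.2.3 scores the DLQI answer 'not at all' as 1, which contradicts its own 0–30 range and DLQI 0/1 endpoint and differs from the SAP, which scores it 0

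*Protocol*

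**What the plan says.** Protocol 5.1.2 lists as a secondary efficacy endpoint: "Proportion of patients achieving a Dermatology Life Quality Index (DLQI) of 0 or 1 at Week 16".

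Protocol 5.2.3 gives the item scoring: "Item scores range from 0 (not relevant) and 1 (not at all) to 3 (very much"). It adds: "Question 7 is a “yes”/ “no” question where “yes” is scored as 3". No value is given for 'a little' or 'a lot'. The same section then says: "DLQI total score is calculated by summing the scores of each question resulting in a range of 0 to 30 where 0-1 = no effect", with 6–10 labelled a moderate effect.

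SAP 10.1 keeps the 0–30 range and the same bands but scores the items differently: "Every item score ranges from 0 (Not relevant/Not at all) to 3 (Very much"). It too gives no value for 'a little' or 'a lot', and none for 'yes' on question 7.

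The form is Figure 10.2: 3 of the protocol. Question 1 ("Over the last week, how itchy, sore, painful or stinging has your skin been") and question 2 ("Over the last week, how embarrassed or self conscious have you been because of your skin") offer four answers, from 'very much' to 'not at all'. Questions 3 to 10, for example question 4 ("Over the last week, how much has your skin influenced the clothes you wear"), also have a 'not relevant' box.

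**The concern.** The endpoint counts patients with a total of 0 or 1. A patient whose skin causes no trouble will answer 'not at all' to questions 1 and 2, because the form offers nothing lower. If that answer is worth 1, two points are already on the total and the patient cannot be a responder. The rule also leaves a single whole number, 2, for two ordered answers ('a little' and 'a lot').

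Anyone scoring complete forms by the protocol sentence would find no responders in either arm, whatever the treatments did, and the risk difference would carry no information. The baseline DLQI summary planned in SAP 10 depends on the same scoring. SAP 10.1 has a different rule, so two documents in force for one trial disagree on what the score is.

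**Working it through.** **Inputs**

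| Answer | Protocol 5.2.3 | SAP 10.1 |
|---|---|---|
| Very much | 3 | 3 |
| A lot | not given | not given |
| A little | not given | not given |
| Not at all | 1 | 0 |
| Not relevant (questions 3–10 only) | 0 | 0 |
| Question 7 'yes' | 3 | not given |

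The total is the sum of the ten items.

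**1. The stated range of 0 to 30.** The domain maxima, identical in both documents, give 4 × 6 + 2 × 3 = 30. The SAP minimum is 10 × 0 = 0. SAP scoring therefore reproduces 0–30.

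**2. The range under the protocol's item rule.** The lowest answer is 'not at all' (1) on questions 1 and 2, and 'not relevant' (0) on questions 3 to 10. The minimum is 1 + 1 + 8 × 0 = 2 and the maximum is still 30, so the range is 2–30. The stated range is not reproduced. The unspecified middle answers do not matter: setting 'a little' and 'a lot' to 2 and 2, 1 and 2, 1.5 and 2.5, or 1.67 and 2.33 gave 2–30 each time.

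**3. 'Not at all' on every item** (question 7: 'no', then 'not at all').
- Protocol: 10 × 1 = 10, the top of its moderate-effect band and a non-responder.
- SAP: 10 × 0 = 0, a responder.

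If question 7 'no' were read as 0, the protocol total would be 9 × 1 + 0 = 9, in the same band.

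**4. Count of complete answer patterns.** Two questions with four answers and eight with five give 4² × 5⁸ = 6,250,000 patterns.
- Protocol rule, both middle answers set to 2: 0 patterns total 0 or 1.
- SAP rule, 'a little' = 1 and 'a lot' = 2:
  - Total 0: 2⁸ = 256, because questions 3–10 each have two zero-scoring answers.
  - Total 1: 2 × 256 = 512 with the single point on question 1 or 2, plus 8 × 2⁷ = 1,024 with it on questions 3–10.
  - Together: 256 + 512 + 1,024 = 1,792.

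These are counts of possible forms, not expected response rates. They show only that the endpoint can be reached under one rule and not under the other.

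**5. Incomplete forms.** If question 1 or 2 is blank and the SAP rule of summing the five remaining domains is applied, the first domain drops out and the protocol-scored minimum becomes 0. With a blank in any other domain, questions 1 and 2 still count and the minimum stays at 2. Protocol 5.2.3 does not say how a total is formed when one domain is missing.

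**The case against.** The strongest reply is that the SAP governs the analysis and its rule works. It scores 'not at all' as 0 and defines the total as the sum of the question scores, so the endpoint is reachable. The protocol's own range and 0–1 band point the same way, which makes its sentence look like a drafting slip. This stands, and it limits the point to a conflict between documents.

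Three stronger readings are tempting, and the documents do not support them.

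- *The planned analysis will show 0% responders in both arms.* That follows only if complete forms are scored by the protocol sentence, and the SAP does not plan that.
- *Totals on two scales will be mixed because sites score the form.* The form has a 'Score' box, but no section tells sites to fill it in or says that its content is entered in the database. Protocol 6.1 has the patient complete the DLQI. SAP 10 describes the baseline PASI as collected in the eCRF but does not say so of the DLQI, for which SAP 10.1 gives a derivation. That suggests, without proving, that the DLQI total is derived.
- *The SAP changed the rule without saying so.* This cannot be shown. The available SAP text passes from section 3.2 to 4.1 and from 16.6 to 19, so a statement of changes could lie in what is missing.

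The stakes are also modest. The synopsis says secondary efficacy results will be interpreted descriptively, and the equivalence decision does not use the DLQI.

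The SAP does not settle everything, however. Its derivation fixes only the two ends of the item scale. Values of 1 and 2 for the middle answers can be inferred from four ordered levels between 0 and 3, and 'yes' = 3 from the question 7 domain maximum, but neither is written there. A programmer who looks for the question 7 value finds it stated only in protocol 5.2.3, beside the faulty score for 'not at all'.

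**Conclusion.** The scoring sentence in protocol 5.2.3 is wrong by the protocol's own figures. On complete forms it gives a range of 2–30 where the same section states 0–30, and it excludes the values 0 and 1 that define the secondary endpoint. For a patient answering 'not at all' throughout, the two documents differ by 10 points and in responder status.

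The consequence is limited. An analysis that uses the SAP values throughout is sound on this point. What remains is one named secondary endpoint with two conflicting scoring rules, and a SAP derivation that leaves three item values unstated. The conclusion rests on the answer boxes printed on the form, on complete forms (a blank on question 1 or 2 is the exception shown above), and on no assumption about the middle answers beyond their scoring at least as high as 'not at all'. Whether anyone scores by the protocol rule in practice is not known from the documents.

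**What to change.** 1. Correct protocol 5.2.3 so that 'not at all' = 0 and 'not relevant' = 0. If no amendment is open, record the correction in the SAP.
2. List every item value in SAP 10.1: very much 3, a lot 2, a little 1, not at all 0, not relevant 0, question 7 'yes' 3. These values fit the stated domain maxima and the 0–30 range.
3. Confirm that any total held in the eCRF or entered by a site follows this list, or state that it is not used.

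The SAP text is a few lines, and the eCRF check is a single query to data management. A protocol amendment made for this alone would cost more: under protocol 8.1 it needs ethics committee and authority approval, for about 50 sites in about 10 countries. SAP 15.1.2.2 also indicates that about 90% of subject data up to Week 16 had been used to fix the burn-in, so much of the Week 16 data was already in hand by SAP version 2.0. The SAP route is therefore the proportionate one unless the protocol is being amended anyway.

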5.3 ASSESSMENT OF SAFETY

At the Screening Visit, the medical examination will include documentation of subject information, informed consent, demographics including height and body weight, smoking and alcohol history, relevant medical history and concomitant therapy, review of inclusion and exclusion criteria, review of vital signs (blood pressure, pulse rate, temperature), 12-lead ECG, laboratory tests (including virus screening, IGRA/PPD test [where applicable], pregnancy test for females), and a physical examination.

On all other visits, it will include review of vital signs, 12-lead ECG, laboratory tests (including IGRA at SFU), pregnancy test for females and a physical examination.

Adverse events and concomitant therapies will be assessed throughout the trial.

Whenever possible, the same person should perform the physical examination throughout the trial (i.e., for all patients at each trial site).

5.3.1 Physical examination

A physical examination will be performed at the visits indicated in the [Flow Chart](#).

The physical examination will include assessment of general appearance, skin, head, neck, throat, lymph nodes, cardiovascular and neurological systems, thyroid gland, musculoskeletal system/limbs, respiratory tract and abdomen.

Clinically relevant abnormal findings will be reported as Baseline conditions or AEs.

5.3.2 Vital Signs

Vital signs will be assessed at the visits indicated in the [Flow Chart](#).

Blood pressure and pulse rate measurements should be taken following at least 5 minutes rest while the patient is in a sitting position. The patient's body temperature will also be recorded. The method of measuring body temperature (oral/aural) should be consistent at a specific trial site.

The investigator must assess all vital signs findings and if the investigator finds any clinically relevant abnormalities, these must be reported as AEs / SAEs as appropriate.

5.3.3 Safety laboratory parameters

The laboratory tests listed in [Table 5.3.3: 1](#) will be analyzed by a central laboratory. The central laboratory provider will also provide the materials for blood sampling. Instructions for the labeling, storage, and shipment of the samples as well as details of all blood variable units and reference ranges can be found in the Laboratory Manual.

Pregnancy testing will be performed by a central laboratory using serum at Screening and local laboratory using urine at all applicable visits thereafter.

For time points of laboratory sampling, see the [Flow Chart](#).

Laboratory results (i.e., all safety laboratory and clinical laboratory data relevant for current clinical practice) of the patients will be available to the respective investigator (via laboratory reports) and to the sponsor (via the central laboratory website) and selected abnormal laboratory alerts will be flagged to the site and sent to sponsor in real time.

The investigator must assess all laboratory results, evaluate any change in laboratory values, and review all clinical laboratory tests for potential clinical significance at all time points throughout the trial. The investigator should endeavor to provide a reason for all out-of-range results deemed not clinically significant. If the investigator determines a laboratory abnormality to be clinically significant, it will be considered an AE / SAE (see Section 5.3.6.1); however, if the laboratory value abnormality is consistent with a current diagnosis, it will be documented accordingly.

Table 5.3.3: 1 Laboratory tests

Category	Test name
Haematology	Hct Hb RBC count / erythrocytes White blood cells / leukocytes Platelet count / thrombocytes
Diff. Automatic	Neutrophils (relative count) Lymphocytes (relative count)
Diff. Manual (if Diff Automatic is abnormal)	Neutrophils, bands (stabs) Neutrophils, polymorphonuclear Lymphocytes
Enzymes	AST (GOT) ALT (GPT) Creatine Kinase CK-MB, only if CK is elevated Gamma-Glutamyl Transferase (GGT)
Electrolytes	Calcium Sodium Potassium Chloride
Substrates	Glucose Creatinine Bilirubin total Bilirubin direct (if total is elevated) Bilirubin indirect (if total is elevated) Total protein Albumin Cholesterol, total
Urine Pregnancy test (only for female patients of childbearing potential) at randomization and continued as indicated in the Flow Chart (including EoT and End of Observational Period Visit)	Human Chorionic Gonadotropin in the urine
Serum Pregnancy test (only for female patients of childbearing potential) at screening and if urine pregnancy test is positive)	Human Serum Chorionic Gonadotropin
Urinalysis (dipstick)	Urine Protein Urine Glucose Urine RBC / erythrocytes
Screening for infections (only at screening)	HBsAg (qualitative) Hepatitis C antibodies (qualitative) HIV-1, and HIV-2 antibody (qualitative, where mandated by local authorities at the discretion of the investigator where clinically indicated)
Screening for infections (only at screening and EoT Visit)	TB test (IGRA: QuantiFERON [®] Gold assay/T-SPOT [®] .TB) (PPD skin test at the discretion of the investigator where clinically indicated) ¹

Abbreviations: ALT=alanine aminotransferase; AST=aspartate aminotransferase; CK-MB=Creatine Kinase-MB; EoT=End of Treatment; Gamma- GGT=Glutamyl Transferase; GOT=Glutamic-Oxaloacetic Transaminase; GPT=Glutamic-Pyruvic Transaminase; Hb=hemoglobin; Hct=hematocrit; HIV=human immunodeficiency virus; IGRA=interferon gamma-release assay; PPD=purified protein derivative; TB=tuberculosis.

¹ There is the trial site option to perform a PPD skin test, although this will not be provided or performed at Central Lab.

5.3.4 Electrocardiogram

The 12-lead ECGs will be performed as scheduled in the [Flow Chart](#).

ECGs will be recorded after the patients have rested for at least 5 minutes in a supine position and will always precede blood sampling.

ECGs may be repeated for quality reasons and the repeat used for analysis. Additional ECGs may be recorded for safety reasons. Clinically relevant, abnormal findings will be reported as AEs.

Information about the details of ECG collection and the parameters assessed will be provided in the ISF.

The original ECG traces and variables must be stored in the patients' medical record as source data. A physician familiar with interpretation of ECG will evaluate the ECG from a clinical perspective and the result (whether the ECG result is normal, abnormal not clinically relevant or abnormal clinically relevant) will be recorded in the appropriate section of the eCRF.

5.3.5 Other safety parameters

5.3.5.1 Local tolerability

The assessment of injection site reactions will be done by the blinded investigator/designee according to "swelling", "hardening", "heat", "redness", "pain", "itching", "bruising", or "other symptoms". If any injection site reactions are observed, these findings should also be reported on the AE eCRF page.

5.3.6 Assessment of adverse events

5.3.6.1 Definitions of AEs

Adverse event

An AE is defined as any untoward medical occurrence in a patient or clinical investigation subject administered a medicinal product and which does not necessarily have to have a causal relationship with this treatment.

An AE can therefore be any unfavorable and unintended sign (including an abnormal laboratory finding), symptom, or disease temporally associated with the use of a medicinal product, whether or not considered related to the medicinal product.

Adverse reaction

An adverse reaction is defined as a response to a medicinal product which is noxious and unintended. Response in this context means that a causal relationship between a medicinal product and an adverse event is at least a reasonable possibility. Adverse reactions may arise from use of the product within or outside the terms of the marketing authorization or from

occupational exposure. Conditions of use outside the marketing authorization include off-label use, overdose, misuse, abuse, and medication errors.

Serious adverse event

An SAE is defined as any AE which:

- results in death,
 - is life-threatening, which refers to an event in which the patient was at risk of death at the time of the event; it does not refer to an event that hypothetically might have caused death if more severe.
 - requires inpatient hospitalization or
 - prolongation of existing hospitalization,
 - results in persistent or significant disability or incapacity, or
 - is a congenital anomaly / birth defect,
- or
- is deemed serious for any other reason if it is an important medical event when based on medical judgment which may jeopardise the patient and may require medical or surgical intervention to prevent one of the other outcomes listed in the above definitions.

Medical and scientific judgement should be exercised in deciding whether other situations should be considered serious reactions, such as important medical events that might not be immediately life threatening or result in death or hospitalization but might jeopardize the patient or might require intervention to prevent one of the other outcomes listed above. Examples of such events are intensive treatment in an emergency room or at home for allergic bronchospasm, blood dyscrasias or convulsions that do not result in hospitalization or development of dependency or abuse. Any suspected transmission via a medicinal product of an infectious agent is also considered a serious adverse reaction.

AEs considered “Always Serious”

Cancers of new histology and exacerbations of existing cancer must be reported as a serious event regardless of the duration between discontinuation of the drug and the occurrence of the cancer.

In accordance with the European Medicines Agency initiative on Important Medical Events, BI has set up a list of further AEs, which by their nature, can always be considered to be “serious” even though they may not have met the criteria of an SAE cited above.

A copy of the latest list of “Always Serious AEs” can be found in the ISF and eCRF. These events should always be reported as SAEs as described above.

Adverse events of special interest

The term AESI relates to any specific AE that has been identified at the project level as being of particular concern for prospective safety monitoring and safety assessment within this trial, e.g., the potential for AEs based on knowledge from other compounds in the same class.

AESI need to be reported to the sponsor's/sponsor designee Pharmacovigilance Department within the same timeframe that applies to SAE, please see above.

The following are considered as AESIs:

1. Hepatic injury

A hepatic injury is defined by the following alterations of hepatic laboratory parameters:

- an elevation of AST and/or ALT \geq 3-fold ULN combined with an elevation of total bilirubin \geq 2-fold ULN measured in the same blood draw sample, and/or
- marked peak aminotransferase (ALT, and/or AST) elevations \geq 10-fold ULN

These lab findings constitute a hepatic injury alert and the patients showing these lab abnormalities need to be followed up according to the "DILI checklist" provided in the ISF. In case of clinical symptoms of hepatic injury (icterus, unexplained encephalopathy, unexplained coagulopathy, right upper quadrant abdominal pain, etc.) without lab results (ALT, AST, total bilirubin) available, the Investigator should make sure these parameters are analyzed, if necessary in an unscheduled blood test. Should the results meet the criteria of hepatic injury alert, the procedures described in the DILI checklist should be followed.

2. Anaphylactic reactions

3. Serious infection (defined as infections requiring IV antibiotics or meeting the regulatory definition of a SAE)

4. Hypersensitivity reactions

Intensity of AEs

The intensity of the AE should be judged based on the following:

Mild:	Awareness of sign(s) or symptom(s) that is/are easily tolerated
Moderate:	Sufficient discomfort to cause interference with usual activity
Severe:	Incapacitating or causing inability to work or to perform usual activities

Causal relationship of AEs

The definition of an adverse reaction implies at least a reasonable possibility of a causal relationship between a suspected medicinal product and an AE. An adverse reaction, in contrast to an AE, is characterised by the fact that a causal relationship between a medicinal product and an occurrence is suspected.

Medical judgment should be used to determine the relationship, considering all relevant factors, including pattern of reaction, temporal relationship, de-challenge or re-challenge, confounding factors such as concomitant medication, concomitant diseases and relevant history.

Arguments that may suggest that there is a reasonable possibility of a causal relationship could be:

- The event is consistent with the known pharmacology of the drug
- The event is known to be caused by or attributed to the drug class.
- A plausible time to onset of the event relative to the time of drug exposure.
- Evidence that the event is reproducible when the drug is re-introduced
- No medically sound alternative aetiologies that could explain the event (e.g., pre-existing or concomitant diseases, or co-medications).
- The event is typically drug-related and infrequent in the general population not exposed to drugs (e.g., Stevens-Johnson syndrome).
- An indication of dose-response (i.e., greater effect size if the dose is increased, smaller effect size if dose is diminished).

Arguments that may suggest that there is no reasonable possibility of a causal relationship could be:

- No plausible time to onset of the event relative to the time of drug exposure is evident (e.g., pre-treatment cases, diagnosis of cancer or chronic disease within days / weeks of drug administration; an allergic reaction weeks after discontinuation of the drug concerned).
- Continuation of the event despite the withdrawal of the medication, taking into account the pharmacological properties of the compound (e.g., after 5 half-lives).
- Of note, this criterion may not be applicable to events whose time course is prolonged despite removing the original trigger.
- Additional arguments amongst those stated before, like alternative explanation (e.g., situations where other drugs or underlying diseases appear to provide a more likely explanation for the observed event than the drug concerned).
- Disappearance of the event even though the study drug treatment continues or remains unchanged.

